### 8.1 Primary Objectives and Corresponding endpoint/outcome variable(s)

The primary objective and corresponding endpoint/outcome variables for the study are listed in Table 3 below.

Primary objectives	Corresponding endpoint/outcome variable(s)	Sec.
A. To investigate the improvement in hearing with the Ponto 3 SuperPower for patients with CHL/MHL.	1. Functional gain with Ponto 3 SuperPower, i.e. the difference between average unaided AC thresholds and aided sound field thresholds as the average (PTA4) of frequencies 500, 1000, 2000 and 4000 Hz	9.3.3.3- 9.3.3.4

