#### 9.3.3.4 Functional gain

The functional gain is a calculation and uses the masked, if not available unmasked, AC thresholds obtained with headphone TDH39 and aided sound field thresholds as described above (9.3.3.1-9.3.3.3). Functional gain is defined as the difference between the unaided AC and aided sound field thresholds. Functional gain can be calculated for frequencies 500Hz, 1kHz, 2 kHz, 3kHz and 4kHz. The average functional gain will be also be calculated for PTA4.

No blocking or masking of the non-implanted ear has been performed during the sound field measurement.

Unaided AC for the implanted ear will be used for the calculation of functional gain. In case of a bilateral Ponto fitting it is the best ear AC that will be used.

The aided soundfield has only been conducted on patients with CHL/MHL, and not for SSD.

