3.1.2 AC and BC audiograms

AC and BC thresholds are measured unmasked and masked for at least one of the ears (commonly the implanted ear). The selection of the AC and BC thresholds depends on the type of hearing loss, as follows:

1. AC thresholds

STATISTISKA KONSULTGRUPPEN		Statistical Analysis Plan	
Protocol: Investigating hearing with Ponto 3 SuperPower, a bone anchored hearing aid - Investigating hearing with Ponto 3 SuperPower, a bone anchored hearing solution.		Protocol No: BC107	Version: 1.0 Page 9 of 23

For CHL/MHL and SSD subjects, AC thresholds are reported using AC unmasked thresholds if the AC masked threshold is not available. No imputations will be used to calculate the average AC thresholds across patients per frequency and the calculation of PTA4 per patient. AC thresholds should be reported for:

- CHL/MHL, unilateral, implanted ear
- CHL/MHL, unilateral, non-BAHS side (if available)
- CHL/MHL, bilateral, both implanted ears (if available)
- SSD, non-implanted ear
- SSD, BAHS side (if available)
- CHL/MHL+SSD (combined group, including SNHL if any), 1) CHL/MHL, unilateral/bilateral, implanted ear; 2) SSD, non-implanted ear; 3) SNHL, unilateral/bilateral, implanted ear

2. BC thresholds

For CHL/MHL and SSD subjects, BC thresholds are reported using BC unmasked thresholds if the BC masked threshold is not available. No imputations will be used to calculate the average BC thresholds across patients per frequency and the calculation of PTA4 per patient. BC thresholds should be reported for:

- CHL/MHL, unilateral, implanted ear
- CHL/MHL, unilateral, non-BAHS side (if available)
- CHL/MHL, bilateral, both implanted ears (if available)
- SSD, non-implanted ear
- CHL/MHL+SSD (combined group, including SNHL if any), 1) CHL/MHL, unilateral/bilateral, masked for implanted ear; 2) SSD, unmasked for non-implanted ear; 3) SNHL, unilateral/bilateral, implanted ear

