3.2 Efficacy Variables

3.2.1 Primary Efficacy Variable

Functional gain with Ponto 3 SuperPower, i.e. the difference between unaided AC thresholds and aided sound field thresholds as the (PTA4) of frequencies 500, 1000, 2000 and 4000 Hz for patients with CHL/MHL (ITT_{CHL/MHL} / TP1 / Bilaterally patients) (Objective A).

Unaided AC thresholds is defined as the masked, if not available unmasked, AC thresholds obtained with headphone TDH39. Unaided AC for the implanted ear will be used for the calculation of functional gain. In case of a bilateral Ponto fitting it is the best ear, calculating PTA4 for both ears and then choose the best one, AC that will be used.

Aided sound field thresholds are defined as sound field audiogram obtained as follow-up after Ponto 3 SuperPower fitting. The aided sound field has only been conducted on patients with CHL/MHL.

PTA4 will be calculated as the mean value of all non-missing values. A sensitivity (variable) analysis will be made for patients where all four including frequencies are non-missing.

Also analyse as the proportion of subjects whose performance is better or equal in the unaided to aided comparisons, i.e. have a difference >0, =0 and <0 (Objective H).

STATISTISKA KONSULTGRUPPEN		Statistical Analysis Plan	
Protocol: Investigating hearing with Ponto 3 SuperPower, a bone anchored hearing aid - Investigating hearing with Ponto 3 SuperPower, a bone anchored hearing solution.		Protocol No: BC107	Version: 1.0 Page 10 of 23

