The additional analysis on the connectivity devices will be conducted on the ITT population.

Generally, PTA4 (for functional gain, effective gain, air-to-bone gap, aided sound field audiology, AC- and BC audiology and BC in-situ measurements) will be calculated as the mean value of all non-missing values. Sensitivity analyses will be made for patients where all four including frequencies are non-missing.

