4.2 Missing Data

Missing data (i.e., single questions, single thresholds) will not be imputed and will be disregarded from the analysis.

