4.2.1 Database codings

1. SMART TRIAL codes

The SMART TRIAL codes will be treated as Not A Number (NANs) and will be disregarded from the analysis. Applicable for the BC107 study are:

- .b: Not answered.
- .c: Not answered due to cancel.
- .d: Not answered due to discontinuation in study.
- .e: Not answered due to exclusion.
- .h: Not answered, hidden by show rule(s).
- .n: Marked as 'Answer not available'.
- .ns: Possibility not selected.

2. 999: Data not measurable

The code is used for sound field audiology, AC- and BC thresholds (i.e., if a threshold is not measurable the code '999' must be entered manually by the investigator). The code will be treated as Not A Number (NANs) and will be disregarded from the analysis.

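### Thresholds coded 999 (not measurable) are deleted like missing data; if the code means no response at the test limit, functional gain can shift, and the planned complete-case check cannot bound it

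*SAP*

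**What the plan says.** SAP 4.2.1 lists the data-capture codes for unanswered items and, separately, code 999, which the investigator enters by hand when a sound-field, AC or BC threshold cannot be measured. Both kinds are handled alike. For 999 the text is: "The code will be treated as Not A Number (NANs) and will be disregarded from the analysis". SAP 4.2 adds: "Missing data (i.e., single questions, single thresholds) will not be imputed and will be disregarded from the analysis". Protocol 11.4 also rules out imputation.

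For the primary variable, SAP 3.2.1 states "PTA4 will be calculated as the mean value of all non-missing values" and sets no minimum number of frequencies. For bilateral fittings the unaided ear is picked by "calculating PTA4 for both ears and then choose the best one, AC that will be used".

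The related check is in SAP 4.1: "Sensitivity analyses will be made for patients where all four including frequencies are non-missing". SAP 4.6.1 uses that complete-case set for the figures and names the mean and 95% CI of functional gain as the main outcome.

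Two further rules bear on the point. SAP 3.1.2 says "AC thresholds are reported using AC unmasked thresholds if the AC masked threshold is not available". On how the gain is averaged, protocol 9.3.3.4 says "The average functional gain will be also be calculated for PTA4", while the endpoint in protocol 8.1 reads "the difference between average unaided AC thresholds and aided sound field thresholds as the average (PTA4".

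**The concern.** A threshold nobody recorded and a threshold the patient could not reach are different things. The first carries no information about its value. The second, if 999 means no response at the highest level tested, says that the value lies above that level. The SAP separates the two in the database and then merges them in the analysis.

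Under that reading the deleted values are the poorest thresholds, so the average over the remaining frequencies is not neutral. The direction depends on the side on which the code occurs, and the bilateral best-ear choice can flip because it uses the same average. The study aims for around 15 subjects with mixed loss above 55 dB HL (protocol 9.1.1), so such values are plausible, although the documents do not say how many there are. At stake are the location of the reported mean and the coverage of its interval.

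**Working it through.** The plan states no figure here that could be reproduced: the sample size of 55 rests on precedent, and the documents give no 999 rate, SD or test limits. Everything below except the planned three groups of about 15 subjects (protocol 9.1.1; 3 × 15 = 45) is assumed. Thresholds are in dB HL at 500/1000/2000/4000 Hz, and gains are averaged over frequencies present in both conditions.

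**One subject, unaided 999.** Unaided 70/75/85/999, aided 35/35/40/50.
- Plan: (35 + 40 + 45)/3 = 40.0 dB.
- With an AC limit of 100-120, the lost gain is at least 50-70, so PTA4 gain is at least (120 + 50)/4 = 42.5 to (120 + 70)/4 = 47.5 dB.
- The lost gain differs from the mean of the others by D = 10-30 dB. The plan is too low by at least D/4 = 2.5-7.5 dB.

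**One subject, aided 999.** Unaided 70/75/85/95, aided 35/35/40/999.
- Plan: 40.0 dB.
- With a sound-field limit of 70-90, the lost gain is at most 25-5, so PTA4 gain is at most (120 + 25)/4 = 36.25 to (120 + 5)/4 = 31.25 dB.
- D = 15-35 dB. The plan is too high by at least 3.75-8.75 dB.

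**Group mean.** If a fraction f of subjects has one such value, all on the same side, the shift is f × D/4.
- f = 0.10, D = 15: 0.10 × 15/4 = 0.375 dB.
- f = 0.20, D = 25: 0.20 × 25/4 = 1.25 dB.

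**Coverage.** With n = 45 and SD 12.5, SE = 12.5/√45 = 1.863 and the half-width is 2.015 × 1.863 = 3.8 dB. Coverage is the probability that a noncentral t (44 df, noncentrality = shift/SE) lies within ±2.015.
- Shift 0.375: noncentrality 0.201, coverage 94.6%.
- Shift 1.25: noncentrality 0.671, coverage 89.9%.
- Extreme corner (f = 0.30, D = 35, SD 10): shift 0.30 × 35/4 = 2.625 dB, coverage 59.4%; with SD 15, 79.1%.

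**What complete-case can show.** Let g be the plan's gain in affected subjects and m the mean gain in the rest. Main = f·g + (1 − f)·m and complete-case = m, so the gap is f(g − m). The deleted value does not enter.
- f = 0.20, g = 40, m = 40: the gap is 0. With unaided 999s the true mean is at least 40 + 0.20 × (2.5 to 7.5) = 40.5-41.5 dB.
- f = 0.20, g = 40, m = 35: complete-case 35.0, main 36.0, truth at least 36.5-37.5 dB. Complete-case is further from the truth than the main result.

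**Best ear.** Right 60/65/70/999 averages 195/3 = 65.0 and is chosen over left 55/65/70/80 at 270/4 = 67.5. The right ear is the worse one if its 4000 Hz value x satisfies (195 + x)/4 > 67.5, that is x > 75.

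**Averaging rule.** If gain were instead the difference of two separate PTA4s, the unaided example would give 230/3 − 160/4 = 76.7 − 40.0 = 36.7 dB instead of 40.0, so the rule needs to be explicit.

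**The case against.** The strongest reply is that the harm rests on an undefined code and an unknown rate. The SAP says only that the threshold is not measurable; no response at the limit is the natural reading, but it is an inference. If no 999 falls at a PTA4 frequency, nothing changes. This stands, and the point is conditional on it.

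A reader might infer from the extreme corner that the interval is badly invalid. The documents do not support that: 59% coverage needs the highest rate, all codes on the aided side, the largest lost gain and the smallest SD together. Nor can one infer a bias in the device's favour, since unaided and aided codes push in opposite directions. The aided case is also the less likely one in unilateral users, because sound-field testing left the other ear open (protocol 9.3.3.3), so an aided 999 needs no response through either ear.

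SAP table 14A.2.1 shows gain and both thresholds by frequency, and listings 16.2.3 and 16.2.4 cover individual audiograms and gains. These help a reader see which frequency drives PTA4, but the per-frequency means share the deletion and a listing is not a bound. The separate table and listing guideline cited in SAP section 7 was not available and may plan a count, so the statement is limited to the SAP text.

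The averaging question is largely settled: SAP 4.1 applies the mean of non-missing values to functional gain itself, so a confirming sentence is enough.

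Finally, substituting a limit is not always informative. In the unaided example with a limit of 100 and an aided 4000 Hz value of 65 instead of 50, the lower bound is (120 + 35)/4 = 38.75 dB, below the plan's 40.0, and says nothing about bias. The fix has to allow for this.

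**Conclusion.** The point holds in conditional form. SAP 4.2.1 deletes a separately coded result as if it had never been recorded. If 999 means no response at the test limit, that deletion can shift the primary mean in either direction, and the complete-case analysis cannot correct or bound the shift. The size cannot be established from the documents. Under the mid-range assumptions above it is about 0.4-1.25 dB, against an interval half-width of 3.8 dB, with coverage of about 95-90%; it is smaller if codes occur on both sides. Protocol 11.3 sets no pass/fail criterion, so the accuracy of the reported estimate is affected, not a trial decision. It should be fixed because the remedy is cheap and leaves the main analysis alone.

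**What to change.** In SAP 4.2.1:
- Define 999, keep it distinct from missing, and report its count by frequency, ear and condition.
- Confirm that PTA4 functional gain is the mean of the per-frequency gains available in both conditions.
- State whether a masked 999 triggers the unmasked fallback of SAP 3.1.2. If it does, some unaided 999s are replaced, not deleted.

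Keep the current rule as the main analysis and add two sensitivity analyses, reported separately and applied to the best-ear choice as well:
- Unaided-only 999 set to the site's maximum test level at that frequency: a lower bound on that subject's gain.
- Aided-only 999 set likewise: an upper bound.

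Leave out, and count separately, any frequency coded 999 in both conditions, since a difference of two limits bounds nothing. State that an unaided bound below the main result, or an aided bound above it, is uninformative about bias. Note the exception to no imputation in SAP 4.2 and protocol 11.4, and record it in SAP section 6.

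The cost is SAP wording, light programming and a matching protocol edit. The site's audiometer and sound-field limits must be obtained; they are not among the planned data items. The substituted values are bounds, not measurements, and if codes occur on both sides each analysis bounds only the affected subjects, not the group mean.

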4.3 Patient Disposition and Data Sets Analyzed

The number of subjects included in each of the ITT, TP1 and TP2 populations will be summarized totally and by type of hearing loss.

4.4 Protocol Violations/Deviations

Not applicable since this is a retrospective study.

4.5 Demographics and Baseline Characteristics

Demographics and baseline characteristics will be analyzed according to the methods described in section "General Methodology" above, and summarized for the following populations:

- ITT totally and by CHL/MHL and SSD.
- TP2.

STATISTISKA KONSULTGRUPPEN	Statistical Analysis Plan	
Protocol: Investigating hearing with Ponto 3 SuperPower, a bone anchored hearing aid - Investigating hearing with Ponto 3 SuperPower, a bone anchored hearing solution.	Protocol No: BC107	Version: 1.0 Page 14 of 23

- TP1.
- Subset from TP1: Bilaterally fitted CHL/MHL subjects.

4.6 Efficacy Analyses

4.6.1 Primary Efficacy Analysis

The primary analysis on functional gain (PTA4) will be made according to the methods described in general methods above. Paired t-test will be the primary test since the functional gain if the case of normally distributed data and Wilcoxon signed-rank test will be performed If non-normality is shown by Shapiro-Wilk test.

The primary endpoint will be reported as defined in general methodology. The main outcome is the mean and 95% CI.

Figures will be made using the sensitivity analyses (only subjects with all four frequencies present).

Primary endpoint will be analysed for the following populations:

- ITT_{CHL/MHL} (main primary analysis).
- TP1.
- Subset from TP1: Bilaterally fitted CHL/MHL subjects.

4.6.2 Secondary Efficacy Analyses

All secondary efficacy analyses will be described descriptively according to general methods above. Functional gain frequencies, difference in speech recognition score between unaided and aided (AB[s] short list test for SSD patients), effective gain (PTA-4 and frequencies), and GBI scores (from before and after fitting) will be tested statically, see general methods.

4.6.3 Additional Efficacy Analyses

The additional analysis on the connectivity devices will be described descriptively according to general methods above.

4.7 Safety Analyses

4.7.1 Adverse Events

Adverse events will be presented with number of events and number and percentage of subjects having events.

5 INTERIM ANALYSES

No interim analysis will be performed.

6 CHANGES OF ANALYSIS FROM PROTOCOL

No changes of analysis from the protocol were made.

STATISTISKA KONSULTGRUPPEN		Statistical Analysis Plan	
Protocol: Investigating hearing with Ponto 3 SuperPower, a bone anchored hearing aid - Investigating hearing with Ponto 3 SuperPower, a bone anchored hearing solution.	Protocol No: BC107	Version: 1.0	Page 15 of 23

7 LISTING OF TABLE, FIGURES AND LISTINGS

Details of the tables, figures and listings can be found in the Appendix BC107 TFL guidelines (filename: BC107_SAP_Tables_Figures_Listing_Guidelines_version 1.0_2021_11_25).

7.1 Listing of Tables

Table Number	Table Title
14.1.1	Patient Disposition and Data Sets Analyzed (ITT Population, TP1, TP1-Bilateral)
14A.1.2	Demographics and Baseline Characteristics by hearing loss (ITT Population)
14A.1.3	PTA4 AC and PTA4 BC audiogram for implanted and non-implanted ear by population and type of hearing loss (ITT Population)
14A.1.4	AC and BC audiograms for implanted and non-implanted ear by population and type of hearing loss (ITT Population)
14A.2.1	Unaided AC threshold, aided sound field threshold, and functional gain (unaided AC - aided), PTA4 and all frequencies, for the combined group and the CHL/MHL group (ITT Population)
14A.2.2	Unaided AC threshold, aided sound field threshold, and functional gain (unaided AC - aided), PTA4 and all frequencies proportion with a difference >0 , $=0$ and <0 , for the combined group and the CHL/MHL group (ITT Population)
14A.3.1	Aided speech recognition (% correct words) measured with the BKB sentence test by test condition (in quiet or in noise) for the combined group and the CHL/MHL group (ITT Population)
14A.3.2	Aided speech recognition (% correct words) measured with the AB[s] short list test by test condition (in quiet or in noise) for the combined group and the CHL/MHL group (ITT Population)
14A.3.3	Speech recognition (% correct words) measured in quiet and in noise with the AB[s] short list test by test condition (aided, unaided, and aided vs unaided) for the combined group and the CHL/MHL group (only for patients with both measurements) (ITT Population)
14A.4.1	Speech recognition score (% correct words) measured in noise with the AB[s] short list test when speech is directed to the aided ear, and noise is directed to the non-implanted ear by unaided, aided, and aided vs unaided for the combined group and the SSD group (ITT Population)
14A.4.2	Proportion with a difference >0 , $=0$ and <0 , between unaided and aided speech recognition scores (% correct words) measured in noise with the AB[s] short list test when speech is directed to the aided ear, and noise is directed to the non-implanted ear for the combined group and the SSD group (ITT Population)
14A.4.3	Speech recognition score (% correct words) measured in noise with the AB[s] short list test when speech is directed to the non-implanted ear, and noise is directed to the aided ear by unaided, aided, and aided vs unaided for the combined group and the SSD group (ITT Population)

STATISTISKA KONSULTGRUPPEN		Statistical Analysis Plan	
Protocol: Investigating hearing with Ponto 3 SuperPower, a bone anchored hearing aid - Investigating hearing with Ponto 3 SuperPower, a bone anchored hearing solution.		Protocol No: BC107	Version: 1.0 Page 16 of 23

14A.4.4	Proportion with a difference >0 , $=0$ and <0 , between unaided and aided speech recognition scores (% correct words) measured in noise with the AB[s] short list test when speech is directed to the non-implanted ear, and noise is directed to the aided ear for the combined group and the SSD group (ITT Population)
14A.5	Aided sound field threshold, BC in-situ, and effective gain (aided – BC in-situ), PTA4 and all frequencies, for the combined group and the CHL/MHL group (ITT Population)
14A.6	Glasgow Benefit Inventory (GBI) scores in each subscale (General, Social, Physical) and total score collected before and after fitting of the P3SP, and their difference, for the combined group and by type of hearing loss (ITT Population)
14A.7	Sound field thresholds, PTA4 and all frequencies for AC and BC thresholds, and 'air to bone gap' (AC - BC) for the combined group and by type of hearing loss (ITT Population)
14A.8	Holger scores collected pro and post fitting of P3SP, for the combined group and by type of hearing loss (ITT Population)
14A.9	Self-reported usage of connectivity device(s) for the combined group and by type of hearing loss (ITT Population)
14B.1.1	Demographics and Baseline Characteristics by hearing loss (TP1, TP1-Bilateral)
14B.1.2	PTA4 AC and PTA4 BC audiogram for implanted and non-implanted ear by population and type of hearing loss (TP1, TP1-Bilateral)
14B.1.3	AC and BC audiograms for implanted and non-implanted ear by population and type of hearing loss (TP1, TP1-Bilateral)
14B.2.1	Unaided AC threshold, aided sound field threshold, and functional gain (unaided AC - aided), PTA4 and all frequencies, for the CHL/MHL group and the bilateral and unilateral group with only BAHS (TP1, TP1-Bilateral)
14B.2.2	Unaided AC threshold, aided sound field threshold, and functional gain (unaided AC - aided), PTA4 and all frequencies proportion with a difference >0 , $=0$ and <0 , for the CHL/MHL group and the bilateral and unilateral group with only BAHS (TP1, TP1-Bilateral)
14B.3.1	Aided speech recognition (% correct words) measured with the BKB sentence test by test condition (in quiet or in noise) for the CHL/MHL group and the bilateral and unilateral group with only BAHS (TP1, TP1-Bilateral)
14B.3.2	Aided speech recognition (% correct words) measured with the AB[s] short list test by test condition (in quiet or in noise) for the CHL/MHL group and the bilateral and unilateral group with only BAHS (TP1, TP1-Bilateral)
14B.4.1	Glasgow Benefit Inventory (GBI) scores in each subscale (General, Social, Physical) and total score collected before and after fitting of the P3SP, and their difference (TP1)
14B.5.1	Sound field thresholds, PTA4 and all frequencies for AC and BC thresholds, and 'air to bone gap' (AC - BC) for the CHL/MHL group and the bilateral and unilateral group with only BAHS (TP1, TP1-Bilateral)
14B.6.1	Holger scores collected pro and post fitting of P3SP for the CHL/MHL group (TP1)

STATISTISKA KONSULTGRUPPEN		Statistical Analysis Plan	
Protocol: Investigating hearing with Ponto 3 SuperPower, a bone anchored hearing aid - Investigating hearing with Ponto 3 SuperPower, a bone anchored hearing solution.	Protocol No: BC107	Version: 1.0	Page 17 of 23

14C.1.1	Demographics and Baseline Characteristics by hearing loss (TP2)
14C.1.2	PTA4 AC and PTA4 BC audiogram for implanted and non-implanted ear by population and type of hearing loss (TP2)
14C.1.3	AC and BC audiograms for implanted and non-implanted ear by population and type of hearing loss (TP2)
14C.2.1	Speech recognition score (% correct words) measured in noise with the AB[s] short list test when speech is directed to the aided ear, and noise is directed to the non-implanted ear by unaided, aided, and aided vs unaided for the SSD group (TP2)
14C.2.2	Proportion with a difference >0 , $=0$ and <0 , between unaided and aided speech recognition scores (% correct words) measured in noise with the AB[s] short list test when speech is directed to the aided ear, and noise is directed to the non-implanted ear for the SSD group (TP2)
14C.2.3	Speech recognition score (% correct words) measured in noise with the AB[s] short list test when speech is directed to the non-implanted ear, and noise is directed to the aided ear by unaided, aided, and aided vs unaided for the SSD group (TP2) for the SSD group (TP2)
14C.2.4	Proportion with a difference >0 , $=0$ and <0 , between unaided and aided speech recognition scores (% correct words) measured in noise with the AB[s] short list test when speech is directed to the non-implanted ear, and noise is directed to the aided ear
14C.3	Glasgow Benefit Inventory (GBI) scores in each subscale (General, Social, Physical) and total score collected before and after fitting of the P3SP, and their difference (TP2)
14C.4	Holger scores collected pro and post fitting of P3SP from the SSD group (TP2)

STATISTISKA KONSULTGRUPPEN		Statistical Analysis Plan	
Protocol: Investigating hearing with Ponto 3 SuperPower, a bone anchored hearing aid - Investigating hearing with Ponto 3 SuperPower, a bone anchored hearing solution.		Protocol No: BC107	Version: 1.0 Page 18 of 23

